The following endpoints will be assessed for patients in both arms of the study enrolled between 01/01/2022 and 12/31/2023 and comparison will be drawn between the 2 groups:

- 1. DLI rate in number per 100-patient month
- 2. Time to first DLI in days

E. Data Management

Data is collected by the PI and analyzed by our data analyst. Additionally, cost data will be collected via our purchasing analyst who will retain data on number ok kits sent to each patient. Patients will be deidentified for all data collection. Data is stored behind the medical center firewall and encryption software. Data is accessible to the PI, the data analyst and our medical director.

F. Statistical Analysis Plan (SAP)

Study Design:

A randomized controlled trial (RCT) in which patients are randomly assigned to one of two groups:

- a. Silver Dressing Group
- b. Standard Dressing Group

Primary Outcome:

 Rate of driveline infection in number per 100 patient month, defined as number of driveline cultures positive for bacterial infection per 100 months of patients on support.

Secondary Outcome(s):

 Mean time to first driveline infection, defined as a number of days to first positive culture.

Covariates to Control for:

- Body Mass Index (BMI)
- Gender

INTERMACS Level

Statistical Analysis Overview:

The analysis will focus on univariate tests to assess the differences between silver dressing and standard dressing groups, while controlling for covariates such as BMI, gender, and INTERMACS level. The significance level for all analyses will be set at p < 0.05.

Data Cleaning and Assumptions:

- Missing data will be addressed using appropriate techniques, such as multiple imputation or complete case analysis, depending on the nature and extent of missing data.
- Assumptions of normality will be assessed for continuous variables, and non-parametric tests will be considered for non-normally distributed data.

Univariate Analysis:

- For continuous outcomes, descriptive statistics (mean, standard deviation) will be presented
 for each treatment group. Between-group comparisons will be made using a two-sample ttest (if data are normally distributed) or a Mann-Whitney U test (if data are non-normally
 distributed).
- For categorical outcomes, descriptive statistics (frequencies and percentages) will be presented for each group. Between-group comparisons will be conducted using the chisquare test or Fisher's exact test, as appropriate.

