- Univariate analysis will focus on comparing the primary and secondary outcomes between the two treatment groups, without adjusting for covariates.

Multivariate Analysis (Controlling for Covariates):

- Linear regression will be used to compare the treatment effects while adjusting for BMI, gender, and INTERMACS level. These covariates will be included as fixed effects in the model.
- The significance level for all covariates will be set at p < 0.05 in the final model, following a backward elimination procedure, if necessary, to identify the most relevant covariates.

Model Assumptions and Diagnostics:

The assumptions for each regression model will be checked. For linear regression, normality
of residuals, linearity, and homoscedasticity will be assessed.

Sensitivity Analyses:

 Sensitivity analyses will be conducted to evaluate the robustness of the results by varying handling strategies for missing data and by testing the impact of potential outliers.

Statistical Software:

• All analyses will be conducted using SAS version 9.4.

Data Handling and Quality Assurance

- Data is collected by the PI and analyzed by our data analyst. Patients are deidentified for all data collection. Data is stored behind the medical center firewall and encryption software. Data is accessible to the PI, the data analyst and our medical director.
- Outliers and implausible values will be reviewed and resolved.

Reporting

- Results will be reported in accordance with CONSORT guidelines.
- Findings will be disseminated through peer-reviewed publications and conference presentations.

[figure not shown]
Conclusion:

The statistical analysis will provide insight into the comparative effectiveness of silver dressing versus standard dressings while controlling for potential confounders such as BMI, gender, and INTERMACS level. The univariate analysis will provide preliminary insights into dressing effect,

with multivariate models ensuring a more rigorous adjustment for confounding variables. All analyses will be conducted at a significance level of p < 0.05.

References

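### The SAP fixes three adjustment covariates, then allows an untriggered p < 0.05 backward elimination to remove them, so the adjusted model is not pre-specified (minor)

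*Combined protocol and SAP*

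**What the plan says.** All the relevant text is in section F (Statistical Analysis Plan) of the combined document.

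- *Covariates to Control for* lists BMI, gender and INTERMACS level. The *Statistical Analysis Overview* says the arms will be compared "while controlling for covariates such as BMI, gender, and INTERMACS level".
- *Multivariate Analysis*, first bullet: "Linear regression will be used to compare the treatment effects while adjusting for BMI, gender, and INTERMACS level". It continues: "These covariates will be included as fixed effects in the model".
- *Multivariate Analysis*, second bullet: "The significance level for all covariates will be set at p < 0.05 in the final model", and then "following a backward elimination procedure, if necessary, to identify the most relevant covariates".
- *Sensitivity Analyses*: robustness is to be examined "by varying handling strategies for missing data and by testing the impact of potential outliers". Covariate selection is not among the things varied.
- *Conclusion*: the univariate results are called preliminary, "with multivariate models ensuring a more rigorous adjustment for confounding variables".

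The plan does not define what would make elimination necessary. It protects no covariate, does not say that treatment is forced to stay in, and does not require the full-model result to be reported.

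**The concern.** The two bullets of the multivariate section cannot both govern the final model. The first fixes the covariate set in advance. The second lets each covariate's p-value in this sample decide whether it stays. In a randomised trial, covariates are adjusted for because they were judged prognostic beforehand, and a p-value above 0.05 in one modest sample is weak evidence against that judgement.

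Two things are at stake. First, the reported adjusted effect may not be adjusted for BMI, gender and INTERMACS level, although the Conclusion says it will be. Second, because the trigger is undefined, whether to eliminate at all is decided after the data are seen, so the SAP does not determine which adjusted estimate is the planned one.

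**Working it through.** **What can be reproduced.** The documents give no sample size, event count or covariate effect, so there is no planned figure to reproduce. The only numerical input is the 0.05 threshold ("The significance level for all covariates will be set at p < 0.05 in the final model"; the general level is also 0.05: "The significance level for all analyses will be set at p < 0.05"). Everything below rests on these assumptions: N = 60, 100 or 150 in total, 1:1 allocation, treatment forced in, and three independent covariates entered as one term each, all with the same correlation r with the outcome.

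**Step 1. No covariate is prognostic.** Each is dropped with probability 0.95, so all three go with probability 0.95³ = 0.857, at any N.

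**Step 2. Chance that all three survive.** All three survive only if each is significant in the full model.

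- Partial correlation of one covariate given the other two: ρ = r / √(1 − 2r²).
- Chance of keeping it (Fisher z; the other two covariates and treatment are conditioned on, hence N − 3 − 3): k ≈ Φ(z − 1.96) + Φ(−z − 1.96), with z = atanh(ρ) × √(N − 6).
- Chance that all three survive: about k³.

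Example, r = 0.3 and N = 60: ρ = 0.3/√0.82 = 0.331; z = 0.344 × √54 = 2.53; k ≈ Φ(0.57) = 0.716; k³ ≈ 0.37.

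The formula agrees with simulated backward elimination (3,000 to 4,000 trials per setting, normal outcome, no treatment effect):

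| N | r = 0.1, formula / simulated | r = 0.2, formula / simulated | r = 0.3, formula / simulated |
|---|---|---|---|
| 60 | 0.15% / 0.2-0.3% | 4.0% / 5% | 37% / 38-40% |
| 100 | 0.5% / 0.6-0.7% | 15% / 16% | 77% / 78-79% |
| 150 | 1.2% / 1% | 37% / 38% | 96% / 96% |

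**Step 3. Does losing covariates cost precision?** Compare the variance of the treatment effect after elimination with its variance when all three are kept.

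- r = 0.1, N = 60: none survives in about 68-69% of trials, and the variance ratio is 0.99. Across all three N at r = 0.1 the ratio is 0.99 to 1.01.
- r = 0.3, N = 60: none survives in about 3%, and the ratio is about 1.08, the largest seen.
- r = 0.3, N = 100 and 150: none survives in 0.2% and 0%.

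Total loss of adjustment is thus common where it costs nothing and rare where it would cost something.

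**Step 4. Type I error and power.** Simulated type I error is 4.5-6.1% with elimination and 4.2-5.8% with all three kept (Monte Carlo standard error about 0.35 points). In a separate set of simulations defined by regression coefficients, the largest gap in a single setting was 6.0% against 5.1%, at N = 60 with coefficients of 0.3 on a unit residual SD. With a treatment effect of 0.6, N = 60 or 100 and coefficients of 0.2 or 0.3, power with elimination minus power with all kept was +1.3, −0.1, −0.1 and −0.4 points, with no consistent loss. Using per-patient infection rates as the outcome, the largest type I gap was 0.6 points (6.0% against 5.5%).

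**The case against.** The strongest reply is that this is a drafting inconsistency with little statistical consequence. Elimination is conditional and may never be run. Randomisation protects the treatment estimate from material bias whichever covariates stay in. The type I and power figures above barely move. The *Statistical Analysis Overview* also puts its emphasis on univariate tests, so the adjusted model may not supply the primary p-value at all. Most of this stands, and it is why the point is graded minor. It does not remove the conflict: an undefined trigger adds discretion, and the Conclusion still presents the multivariate model as the more rigorous analysis.

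Three stronger readings are tempting, and the documents do not support them.

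- *A reader might infer that the adjusted analysis will often, or usually, be no adjustment.* That needs N and covariate strength, which are not given. At r = 0.3 and N = 150, all three survive in 96% of trials.
- *A reader might join the 68-69% chance of losing every covariate to the 8% variance loss and see one harm.* They come from opposite ends of the assumed range (r = 0.1 and r = 0.3) and do not occur together.
- *A reader might blame elimination for the inflation from picking the best of several models.* Taking the smallest p-value from the unadjusted, full and eliminated models gives 6.5-8.2% for r = 0.1 to 0.3, but the unadjusted and full models alone already give 6.3-7.7%. Nearly all of it comes from having no designated primary analysis. That is a separate issue, and deleting the elimination sentence does not solve it.

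A fair practical objection also stands: if events are few, entering INTERMACS level as a many-category factor could make a count or survival model unstable. The fix allows for this.

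**Conclusion.** The inconsistency is real and follows from the text alone: one bullet fixes the covariate set and the next lets the data choose it, with no rule for when. The adjusted model is not pre-specified and may not deliver the adjustment the Conclusion describes. That holds at any sample size.

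The size of the effect is modest. The loss of precision is at most about 8% in variance and near zero for weak covariates; the rise in type I error is at most about 1 point. These figures assume 60 to 150 patients, three independent single-term covariates with correlations of 0.1 to 0.3, and mainly a normal outcome in a linear model. The case for change rests on pre-specification, not on bias or lost power. Severity: minor. Whether linear regression suits a rate or a time to first infection is a separate question, not judged here.

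**What to change.** Delete the backward-elimination sentence from *Multivariate Analysis* and replace it with: 'The adjusted model contains treatment, BMI, gender and INTERMACS level, all retained whatever their p-values.' Apply this to whatever regression model is finally used.

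State in advance how INTERMACS level is coded, in a low-dimensional form such as one ordinal term or a few grouped categories, so that the model stays stable if infections are few.

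The cost is this small SAP edit and a few degrees of freedom. The three covariates are already named in the plan, so the change adds no variable and needs no further patients. The simulations behind this point used linear models only, so stability in a sparse-event count or survival model has not been shown; the coding rule is there to guard against that.
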